9.7 Pharmacogenomics

Not applicable.

9.7.1 ADME Sampling

Not applicable.

9.8 Biomarkers

. Additional biomarkers related to mechanism of action, such as, but not limited to safety biomarkers, and associations with response to BMS-986249 alone and in combination with nivolumab, ipilimumab in combination with nivolumab, and nivolumab monotherapy will be explored.

If biomarker samples are drawn but study treatment(s) is not administered, samples will be retained. A detailed description of each biomarker sample analysis and assessment is described below, and a schedule of biomarker sample collections is provided in Table 9.8.3-1. Further details of blood, serum, and tumor tissue collection and processing will be provided to the site in the Laboratory Manual.

Addendum per Protocol Amendment 09: Biomarker sample collection after has been reduced to decrease participant and site burden as available sample collections are sufficient for proposed analysis of the exploratory endpoint.

9.8.1 Peripheral Blood Biomarkers

A variety of factors that may impact the immunomodulatory properties and efficacy of BMS-986249, ipilimumab, and nivolumab will be investigated in peripheral blood specimens taken from all participants prior to or during treatment at the time points indicated in Table 9.8.3-1. Results from these investigations will be evaluated for associations with dose, response, survival, and/or safety (AE) data. Several analyses will be completed and are described briefly below.

9.8.1.1 Soluble Biomarkers

Serum samples as well as blood samples used for PK analysis may also be used to evaluate circulating levels of immune factors, such as , over the course of the treatment.

9.8.1.2 Immunophenotyping

The proportion of specific lymphocyte subsets and expression levels of T cell co-stimulatory markers in PBMC preparations will be quantified by flow cytometry.

9.8.1.3 T cell Repertoire Analysis

The diversity of the peripheral T cell compartment and changes over the course of treatment with immunotherapeutic agents may be related to the mechanism of action of BMS-986249.

9.8.1.4 Germline DNA Variants

Whole blood will be collected from all participants prior to treatment to generate genomic DNA for single nucleotide polymorphism (SNP) analyses and to serve as a reference for tumor genomic testing, including tumor mutational load assessment.

9.8.2 Tumor Samples

Tumor biopsy specimens will be obtained from all participants to characterize immune cell populations and expression of selected tumor markers including, dMMR and MSI-H. See Section 2 and Table 9.8.3-1 for the tumor collection schedule time points. Pre-treatment biopsy tissue required for all participants. Refer to Table 2-1 and Laboratory Manual for details.

- For Part 1: The on-treatment biopsy will be collected on and, and tumor specimens may be collected within 3 days of the specified time point and must be obtained prior to administration of study treatments. Bone lesion biopsies are unacceptable for submission.
- For Part 2A: Pre-treatment tumor tissue specimens will be submitted for central PD-L1 IHC assessment prior to randomization (refer to Laboratory Manual for details). These biopsy samples should be excisional, incisional, punch or core needle. Fine needle aspirates or other cytology specimens are insufficient for downstream biomarker analyses. PD-L1 stained tissue sections will be assessed by a pathologist and scored as PD-L1 positive if membrane staining is observed in ≥ 1% tumor cells among a minimum of a hundred (100) evaluable tumor cells.

Samples with < 1% tumor cell membrane staining in a minimum of a hundred (100) evaluable tumor cells will be scored as PD-L1 negative and samples where membrane staining is obscured by high cytoplasmic staining or melanin content, but contain the minimum number of evaluable tumor cells will be deemed PD-L1 indeterminate.

For Part 2A: The on-treatment biopsy will be first collected on for approximately the
first 75 participants treated (about 25 participants per active Arm), and then collected per
Investigator preference on or for approximately the next 105 participants treated
(about 35 participants per active Arm). On-treatment tumor specimens may be collected within
3 days of the specified time point and must be obtained prior to administration of study
treatment. Bone lesion biopsies are unacceptable for submission.

•	For Part 2A.
	. The varying number of participants for
	each of the different timed on-treatment tumor biopsy collections is to enable a sufficient
	number of samples for analysis while accounting for on-treatment attrition and factors related
	to biopsy heterogeneity.

- For Part 2B, the on-treatment biopsy will be collected on . Tumor specimens may be collected within 3 days of the specified time point and must be obtained prior to administration of study treatment. Bone lesion biopsies are unacceptable for submission.
- A tumor biopsy is mandatory upon confirmation of PD (within 7 days) except for:
 - Participants who have an on-treatment biopsy and progress within 4 cycles.
 - Participants who will be imminently (within 4 weeks) enrolling in a subsequent clinical research study that requires a screening biopsy, then the new trial enrollment criteria supersede the required post-progression tumor biopsy.
 - Participants who consent to be treated beyond progression will only require the PD biopsy at the subsequent confirmation of progression.
- Both the screening and on-treatment tumor biopsies should be preferentially collected from the same site, if feasible. At the time of progression, the biopsy should be performed using a progressive lesion or a new lesion, if feasible.
- Tumor biopsy samples should be excisional, incisional, or core needle as fine needle aspirates and other cytology specimens are insufficient for downstream biomarker analyses. Bone lesion biopsies are unacceptable for submission.
- On-treatment and PD biopsies are mandated at acceptable clinical risk (as determined by the investigator). Notify the Medical Monitor (or designee) if on-treatment biopsy may pose unacceptable clinical risk or if tumor at the time of on-treatment biopsy is not accessible for sampling. Institutional guidelines for the safe performance of biopsies should be followed.
- All tumor tissue collection (fresh biopsy or archival) will follow the same guidance methodology for sample collections provided in the Laboratory Manual.

								In addition	on, tissue	biopsies v	will assist
in	characterizing	the	PK	of ipilimumab	and	the	various	Probody	species.		

111111111111111111111111111111111111111	
formalin-fixed, paraffin-embedded and archival tumor specimens may also be made.	veen fresh
9.8.2.1 Characterization of Tumor Immune Microenvironment	
HC will be used to assess the number and composition of immune infiltrates in order the immune cell subsets present within tumor tissue before and after exposure to there	

Biomarker Sampling Schedule 9.8.3

Table 9.8.3-1: Biomarker Sampling Schedule for All Study Parts

Study Day of Sample Collection	Time (Relative to infusion time) Hour:Min	Tumor Biopsy ^a	Serum	Whole Blood (Germline and TCR)	Whole Blood (PAXgene)	Blood (Immuno- phenotyping)	Plasma	Anti- SARS- CoV-2 Serology	
-----------------------------------	---	------------------------------	-------	--------------------------------------	--------------------------	--------------------------------	--------	-------------------------------------	--

Abbreviations: ; PD = progressive disease; SARS-CoV-2 = severe acute respiratory syndrome coronavirus 2; TCR = T cell receptor.

Protocol Amendment No.: 09

For additional information regarding tumor sample collection, refer to Section 2, Section 9.8.2, and Laboratory Manual for details.

9.8.4 Additional Research Collection

This protocol will include both sample collection and residual sample storage for additional research (AR).

For All Sites:

Additional research is required for all study participants, except where prohibited by IRBs/ethics committees, prohibited by local laws or regulations, or academic/institutional requirements.

- If the IRB/ethics committees and site agree to the mandatory additional research retention and/or collection, then the study participant must agree to the mandatory additional research as a requirement for inclusion in the study.
- If optional participation is permitted and approved, then the study participants may opt out of the additional research retention and/or collection.

Additional research is intended to expand the R&D capability at Bristol-Myers Squibb, and will support as yet undefined research aims that will advance our understanding of disease and options for treatment. This may also include genetic/genomic exploration aimed at exploring disease pathways, progression, and response to treatment.

Sample Collection and Storage

All requests for access to samples or data for AR will be vetted through a committee of the study Sponsor's senior leaders in Research and Development to ensure the research supports appropriate and well-defined scientific research activities.

Samples kept for future research will be securely stored at the , or a BMS-approved third-party storage management facility.

The manager of these samples will ensure they are properly used throughout their usable life and will destroy the samples at the end of the scheduled storage period, no longer than 15 years after the end of the study or the maximum allowed by applicable law.

Transfers of samples by research Sponsor to third parties will be subject to the recipient's agreement to establish similar storage procedures.

Samples will be stored in a coded fashion, and no BMS researcher will have access to the key. The key is securely held by the investigator at the clinical site, so there is no direct ability for a BMS researcher to connect a sample to a specific individual.

Further details of sample retention and processing will be provided to the site in the Laboratory Manual. See Table 9.8.4-1 for time points for retention of each sample type.

Sample Type	Time points for which residual samples will be retained
PK/ADA	All
Tumor Biopsy	All
Blood biomarker samples	All

Table 9.8.4-1: Residual Sample Retention for Additional Research Schedule

Abbreviations: ADA = anti-drug antibody; PK = pharmacokinetic.

9.9 Patient-reported Outcomes

Quality of life (QoL) in oncology clinical studies is becoming increasingly important to understand the impact of benefit/risk from the patient perspective. Participants enrolled in the BMS-986249 in Combination with Nivolumab Randomized Cohort Expansion in Melanoma (Part 2A) and Participants enrolled in BMS-986249 in Combination with Nivolumab Additional Tumor Cohort Expansion (Part 2B) will be asked to complete the EORTC QLQ-C30, EQ-5D-3L, FACIT GP5 item, and a selection of items from the PRO-CTCAE prior to first dose, at designated on-treatment clinic visits, and at safety follow-up visits 1, 2 and 3. Only the EQ-5D-3L will be completed, via telephone, during Survival Follow-up Period.

The questionnaires will be provided in the participant's preferred language if available. The EQ-5D-3L may be administered by telephone during survival follow-up. There exists a standardized guide that can be used to facilitate telephone administration of the EQ-5D-3L.

Section 2 provides information regarding the timing of PRO assessments. The questionnaires should be administered at the start of any visit before the participant sees the physician and before any study-related procedures are performed. If exceptional circumstances preclude the continued administration of measures using planned modalities, then alternate administration methods may be required.

9.9.1 **EORTC QLQ-C30**

Health-related QoL will be assessed using the EORTC QLQ-C30⁵⁹. The EORTC QLQ-C30 is a 30-item instrument that has gained wide acceptance in oncology clinical studies and is composed of multi-item and single-item scales. The global health status/QoL scale is composed of 2 items. In addition to the global health status/QoL scale, the EORTC QLQ-C30 includes 5 functional scales (physical, role, emotional, social, and cognitive), 3 symptom scales (fatigue, nausea and vomiting, and pain), and 6 single items (dyspnea, insomnia, appetite loss, constipation, diarrhea, and financial difficulties). The overall health status/QoL responses are 7-point Likert scales ranging from 1 (Very Poor) to 7 (Excellent), while the responses for all functional and symptom items are 4-point categorical scales ranging from 1 (Not at all) to 4 (Very much). Scale items are scored using recommended EORTC procedures. Raw scores are transformed to a linear scale ranging from 0 to 100, with a higher score representing a higher global health status/QoL. A score difference of 10 is used as an estimate of the minimal important difference (MID) for the subscales

of the EORTC QLQ-C30.⁶¹ The reliability and validity of the questionnaire is highly consistent across different language-cultural groups.

9.9.2 EQ-5D-3L

General health status will be measured using the EQ-5D-3L.⁶² The EQ-5D-3L is a standardized instrument used to measure self-reports of health status and functioning. The instruments descriptive system consists of 5 dimensions: mobility, self-care, usual activities, pain/discomfort, and anxiety/depression. Each dimension has 3 levels, reflecting "no health problems", "moderate health problems" and "extreme health problems". A dimension for which there are no problems is said to be at level 1, while a dimension for which there are extreme problems is said to be at level 3. Thus the vectors 11111 and 33333 represent the best health state and the worst health state, respectively. Altogether, the EQ-5D-3L describes 243 different health states. Empirically derived weights can be applied to an individual's response to the EQ-5D-3L descriptive system to generate an index measuring the value to society for that specific health state. Such preference weighting systems have been developed for many geographical areas. In addition, the EQ-5D-3L includes a visual analogue scale (VAS) that allows respondents to rate their own current health on a 100-point scale, ranging from "best imaginable" to "worst imaginable" health. The utility data generated from the EQ-5D-3L is recommended for, and commonly used in, cost effectiveness analyses. A score difference of 0.08 for the EQ-5D utility score and of 7 for the EQ VAS will be used as MID estimates for the EO-5D-3L.⁶³

9.9.3 FACIT GP5

A single item drawn from the FACIT measurement system, item GP5, will be administered to assess the overall extent of perceived bother due to symptomatic adverse events (symAEs). Evidence exists for the validity of this item and its usefulness as an overall summary measure of burden due to symptomatic treatment toxicities.⁶⁴

9.9.4 PRO-CTCAE

Given evidence that clinicians underreport symptomatic AEs, selected items from the PRO-CTCAE will be used to enhance the assessment of symAEs in the study. Items will be chosen based on the known clinical profile of ipilimumab in combination with nivolumab, clinical judgement, experience of the study team members, and what is known for Part 2A and Part 2B treatments.

9.10 Health Economics OR Medical Resource Utilization and Health Economics

Health economics/medical resource utilization and health economics parameters will not be evaluated in this study.

10 STATISTICAL CONSIDERATIONS

10.1 Sample Size Determination

10.1.1 Dose Escalation

Dose escalation in Part 1A (BMS-986249 monotherapy) and Part 1B (BMS-986249 combination therapy with nivolumab) will be guided by BLRM employing the EWOC principle. The BLRM method is fully adaptive; makes use of all the information available at the time of each dose assignment, not just data from the current dose level; and directly addresses the ethical need to control the probability of overdosing. Furthermore, the BLRM uses the knowledge gained from participants treated with ipilimumab (for Part 1A) or ipilimumab in combination with nivolumab (for Part 1B). The use of the EWOC principle limits the risk of exposing participants in the next cohort to an intolerable dose by ensuring that the posterior probability of
the DLT rate exceeding at any dose is capped at
Approximately 4 participants (3 + 1) will be treated at the starting dose levels of BMS-986249 alone or BMS-986249 in combination with nivolumab. While the BLRM will use DLT information from the DLT period only, clinical assessment will take into consideration the entirety of available preliminary data, including PK/ from all treated participants in assigning a dose level for the next cohort of 3 participants. AEs meeting DLT criteria outside of the 5-week DLT period may also be incorporated into the BLRM and dose de-escalation may be considered as appropriate based on the BLRM recommendation. At least 6 DLT-evaluable participants will be treated at the BLRM-recommended MTD (BLRM-MTD). A maximum of 12 DLT-evaluable participants will be treated at each dose level. Once the BLRM-MTD is identified, then additional participants may be treated at the BLRM-MTD or any dose level below the BLRM-MTD for further evaluation of safety, PK, or parameters as required. The maximum number of participants to be treated will be up to 45 for Part 1A (BMS-986249 monotherapy) and up to 60 for Part 1B (BMS-986249 combination therapy with nivolumab).
The BLRM-MTD is the dose that satisfies the following 3 conditions:

- The empirical posterior probability that the "DLT rate of 16% to pre-specified value (ie, 50%).
- This probability needs to be the largest among the dose levels that satisfy the EWOC condition
- A minimum number of participants (ie, 6) was treated at this dose level.

The final MTD/RP2D will be based on the recommendations from the BLRM and overall clinical assessment of all available safety, PK, and efficacy data. Lower doses may be tested if none of the planned doses are found to be tolerable. Such decisions will be made after discussion and agreement between the investigators and the Medical Monitor (or designee).

10.1.2 Part 2A Cohort Expansion

10.1.2.1 Original Sample Size Calculation

The BMS-986249 in Combination with Nivolumab Randomized Cohort Expansion in Melanoma (Part 2A) sample size determination is based on primary efficacy and primary safety objectives.

The sample size estimation takes into consideration:

The potential for detecting a higher ORR in BMS-986249 in combination with nivolumab (Arms A, B, and C) relative to nivolumab monotherapy (Arm E).

The potential for detecting improved tolerability based on incidence of Grade 3-5 TRAEs within 24 weeks in BMS-986249 in combination with nivolumab (Arms A, B, and C) relative to ipilimumab in combination with nivolumab (Arm D).

Approximately 270 evaluable participants will be randomized in a 1:1:1:1:1 ratio to Arms A - E respectively, with at least 54 evaluable participants in each arm. Randomization will be stratified by PD-L1 status and AJCC M-staging. Assuming a ORR in nivolumab monotherapy (Arm E), the two-sided 60% CIs for the difference in ORR comparing each BMS-986249 in combination with nivolumab arm (Arms A, B, and C) versus nivolumab monotherapy for a range of ORRs in BMS-986249 in combination with nivolumab arm (Arms A, B, and C) close to the ORR observed in ipilimumab in combination with nivolumab based on Study CA209067 are presented in difference in ORR if an ORR of or higher is observed in BMS-986249 in combination with nivolumab arm (Arm A, B, and C).

In addition, assuming a incidence rate of drug-related Grade 3-5 AEs within 24 weeks in ipilimumab in combination with nivolumab (Arm D), with 54 evaluable participants in each of BMS-986249 in combination with nivolumab arms (Arm A, B, and C) and ipilimumab in combination with nivolumab arm (Arm D), 60% two-sided CI of treatment difference in incidence rate for each BMS-986249 in combination with nivolumab arm (Arm A, B, and C) versus ipilimumab in combination with nivolumab arm (Arm D) is

incidence rate of drug-related Grade 3-5 AEs within 24 weeks in BMS-986249 in combination with nivolumab arms (Arm A, B, and C). Besides the primary safety endpoint of drug-related Grade 3-5 AEs by within weeks, the safety profile will also be evaluated based on the entirety of available clinical safety data.

The final analysis will take place when all randomized participants have completed at least 36 weeks follow-up or discontinue earlier. Due to exploratory nature of the proof of concept (PoC) design, no multiplicity adjustment will be made for testing multiple endpoints or multiple treatment arms.

10.1.2.2 Changes to Sample Size Assumptions for Revised Protocol 07

[figure not shown]
The original sample size calculation was based on a 60% two-sided CI of ORR for the difference between treatments and required 54 participants per arm. As participants in Arm E will not be randomized as originally planned, the efficacy evaluation and the statistical comparison will use a reference value of based on nivolumab monotherapy historical data in melanoma (see Section 5.4.7.2).

One of the main objectives of this study is to evaluate the preliminary safety and tolerability of BMS-986249 in combination with nivolumab (Part 2A Arm C and Arm F).

Based on final analysis of CA209511, the ipilimimab 3 mg/kg in combination with nivolumab 1 mg/kg, the incidence rate of drug-related Grade 3-5 AEs within 24 weeks is estimated to be relative improvement in the incidence of Grade 3-5 TRAEs is considered to be clinically relevant.

Using a two group $\chi 2$ test with a 0.10 one-sided significance alpha level, assuming a 1:1 randomization ratio of experimental BMS-986249 in combination with nivolumab containing regimen to control ipilimumab in combination with nivolumab, a sample size of 60 participants per arm will have approximately 70% power to detect a ratio in favor of the alternative hypothesis of compared to the null hypothesis proportion of

The null hypothesis is the ratio of proportions above or equal to 1, the alternative hypothesis is the ratio of proportion is below to 1.

Protocol Amendment No.: 09 Date: 14-Mar-2023

e: 14-Mar-2023

The final analysis will take place when all randomized participants have completed at least 36 weeks follow-up or discontinue earlier. Due to exploratory nature of the PoC design, no multiplicity adjustment will be made for testing multiple endpoints or multiple treatment arms.

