To evaluate the preliminary safety and tolerability of BMS-986249 in combination with nivolumab (Arm C and Arm F) relative to ipilimumab in combination with nivolumab (Arm D) in participants with previously untreated, unresectable or metastatic melanoma	• Incidence of treatment-related Grade 3-5 AEs within 24 weeks
To evaluate the preliminary efficacy of BMS- 986249 in combination with nivolumab (Arm C and Arm F) relative to historic nivolumab monotherapy data in participants with previously untreated, unresectable or metastatic melanoma	ORR as assessed by investigator using RECIST v1.1
Secondary	
To assess the anti-tumor activity of BMS-986249 in combination with nivolumab (Arm C and Arm F) and ipilimumab in combination with nivolumab (Arm D) in participants with previously untreated, unresectable or metastatic melanoma	ORR, DOR, PFS, and TTR as assessed by investigator using RECIST v1.1
To assess the safety and tolerability of BMS- 986249 in combination with nivolumab (Arm C and Arm F), and ipilimumab in combination with nivolumab (Arm D) in participants with previously untreated, unresectable or metastatic melanoma	Incidence of AEs, SAEs, AEs leading to discontinuation, death, and laboratory abnormalities
To characterize the PK of BMS-986249 when administered in combination with nivolumab	 Summary measures of PK parameters of BMS-986249 in combination with nivolumab
To evaluate time to deterioration (TTD) in Quality of Life (QoL) and physical functioning	• TTD as defined by a minimally important decrease from baseline ≥10 points on the EORTC QLQ-C30 global health status/quality of life subscale (items 29 & 30) and Physical Functioning Scale (items 1 to 5)
Exploratory	
To explore the associations between PK of BMS-986249, ipilimumab and nivolumab, safety, efficacy, and clinical biomarkers such as, but not limited to T cell-specific genes	Association measures between BMS986249, ipilimumab, and nivolumab PK levels, select outcomes, and biomarkers of interest
BMS-986249, ipilimumab and nivolumab, safety, efficacy, and clinical biomarkers such as, but not	ipilimumab, and nivolumab PK levels, select

Protocol Amendment No.: 09

Date: 14-Mar-2023 78

Table 4-2: Objectives and Endpoints: The Dose Expansion Phase in Melanoma (Part 2A)

Objectives	Endpoints	
To characterize the immunogenicity of BMS-986249, ipilimumab and nivolumab	Incidence of ADA to ipilimumab, nivolumab, and BMS-986249	

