5.2 Number of Participants

- Part 1A Monotherapy Escalation: The total sample size is up to approximately 45 evaluable participants.
- Part 1B Combination Escalation: The total sample size is up to approximately 60 evaluable participants.
- Part 2A Expansion in Melanoma: The total sample size is up to approximately 200 evaluable participants with approximately 60 evaluable participants each treated in Arm C, Arm D, and Arm F, respectively. Prior to Revised Protocol 07, up to approximately 20 evaluable participants may have been enrolled across Arms A, B, and E, collectively. (See Section 10.1.2.)
- Part 2B Additional Tumor Cohort Expansion: The total sample size is up to approximately 120 evaluable participants with approximately 40 evaluable participants per tumor type cohort.

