5.4.7.2 Rationale for Nivolumab Monotherapy as a Reference

In 2 distinct Phase 3 trials, nivolumab monotherapy demonstrated clinical benefit in participants with previously untreated unresectable or metastatic melanoma. ¹² In the Phase 3 trial, CA209066, 3 mg/kg nivolumab monotherapy demonstrated an ORR of 40%, significantly greater than that of dacarbazine alone (14%). ²⁷ In study CA209067, 3 mg/kg nivolumab monotherapy achieved an ORR of 45%, this was numerically lower than ipilimumab in combination with nivolumab, but significantly greater than that of ipilimumab alone. This pattern of response rate was consistent regardless of PD-L1 expression levels (see Table 5.4.7.2-1). ¹²

Table 5.4.7.2-1: CA209067 ORR Result Summary by PD-L1 Expression

	nivolumab (N=316)	nivolumab in combination with ipilimumab regimen (N=314)	ipilimumab (N=315)
Objective Response	141 (45%)	185 (59%)	60 (19%)
ORR by tumour PD-L1 expression < 1%	35%, n=41/117	55%, n=68/123	19%, n=21/113
ORR by tumour PD-L1 expression ≥ 1%	55%, n=94/171	65%, n=101/155	19%, n=31/164

Abbreviations: ORR = objective response rate; PD-L1 = programmed death ligand-1.

In both CA209066 and CA209067, the incidence of AEs was lowest in the nivolumab group, most AEs were low-grade (Grade 1-2) with relatively few drug-related high-grade AEs (Grade 3-4, 15% in CA209066 and 16% in CA209067, see Table 5.4.7.1-1). In addition, the safety profile was consistent with that seen in other tumor types. ^{24,27} These data resulted in nivolumab being approved for use by the U.S. FDA in 2014, Marketing Authorization in Europe in 2015, and additional regions for the treatment of metastatic melanoma. ¹²

Nivolumab monotherapy was initially chosen as a reference arm in Part 2A because it may have allowed for a contemporaneous assessment of the contribution of components and therapeutic index of BMS-986249 in combination with nivolumab.

The dose and schedule of 480 mg nivolumab administered IV Q4W is based on the approved recommended dose in advanced melanoma.²⁶

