5.4.8 Rationale for Part 2A Stratification by M-Staging and PD-L1 Status

In order to minimize the potential for imbalances across treatment arms, participants will be stratified by PD-L1 expression (\geq 1% tumor cell surface expression versus < 1% tumor cell expression/indeterminate), and the AJCC M stage (M0/M1a/M1b versus M1c) in Part 2A. Prognostic implications of M-Staging are well established. Among patients treated with nivolumab monotherapy and the combination of ipilimumab and nivolumab, higher response rates have been observed in patients with PD-L1 tumor expression \geq 1%, thus stratification in this study will ensure better balance in baseline characteristics and will minimize bias in terms of response across treatment groups. 32,33 While both BRAF positive and BRAF wild-type participants are eligible, BRAF status is not a stratification factor.

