PFS PFS for a participant is defined as the time from the first dosing date (Part 1, Part 2B) or randomization date (Part 2A) to the date of first objectively documented disease progression per RECIST v1.1 or PCWG3 or death due to any cause, whichever occurs first.	Median and CI by K-M method and PFS rates
PSA Response Rate (For Part 2B CRPC Participants Only) Decrease in the level of PSA of at least 50% from baseline maintained for at least 3 weeks	Point estimate and CI
TTR TTR is defined as the time from the first dosing date (Part 1, Part 2B) or randomization date (Part 2A) to the date of the first confirmed response (CR or PR) per RECIST v1.1 or PCWG3.	Summary statistics for TTR
OS OS is defined as the time from enrollment (Part1, Part 2B) or randomization (Part 2A) to the date of death from any cause	Median and CI by K-M method (including OS rates, for example at 1 year and 2 years)

Abbreviations: BOR = best overall response; CI = confidence interval; CR = complete response; DOR = duration of response; K-M = Kaplan Meier; ORR = Objective Response Rate; OS = overall survival; PCWG3 = Prostate Cancer Working Group 3; PFS = progression-free survival; PR = partial response; PSA = prostate-specific antigen; RECIST = Response Evaluation Criteria in Solid Tumors; TTR = time to response.

Protocol Amendment No.: 09

^a Efficacy analyses will be executed with a 60% two-sided CI.

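### The primary ORR comparison in Part 2A uses one fixed historical nivolumab rate, although that rate differs by about 20 points by PD-L1, so its meaning depends on the PD-L1 mix enrolled

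*Combined protocol and SAP*

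**What the plan says.** Section 4 (Table 4-2) makes investigator-assessed ORR in Arms C and F a primary endpoint, judged "relative to historic nivolumab monotherapy data in participants with previously untreated, unresectable or metastatic melanoma". Section 10.1.2.2 explains that, because Arm E will not be randomised as planned, "the efficacy evaluation and the statistical comparison will use a reference value of" a figure based on historical nivolumab monotherapy, and points to Section 5.4.7.2. The figure itself is redacted, which is no fault of the plan.

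Section 5.4.7.2 reports nivolumab ORRs of 40% (CA209066) and 45% (CA209067). Its table splits the CA209067 result by PD-L1. Section 5.4.8 says that "participants will be stratified by PD-L1 expression" and M-stage, partly because "higher response rates have been observed in patients with PD-L1 tumor expression" of at least 1%. Section 5.2 plans "approximately 60 evaluable participants each treated in Arm C, Arm D, and Arm F, respectively", and the footnote to Table 10.3.1-1 says "Efficacy analyses will be executed with a 60% two-sided CI".

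Table 4-4 and Section 10.3.1 add stratified (Cochran-Mantel-Haenszel) analyses of ORR. The visible text contains no PD-L1 enrolment quota, no reference by PD-L1 stratum and no weighted reference.

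**The concern.** The plan treats PD-L1 as important enough to balance between randomised arms, yet the benchmark for the primary efficacy objective takes no account of it. Stratified randomisation and Cochran-Mantel-Haenszel methods protect comparisons between concurrent arms. They cannot adjust a comparison with a constant.

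If Arms C and F enrol a larger PD-L1 ≥ 1% share than the population behind the reference, nivolumab alone would be expected to exceed that reference, and a combination that adds nothing could look active. The protocol itself raises the possibility of a different population. Section 5.4.7 warns that historical controls may not represent current patients, and Section 5.4.7.2 says that people willing to be randomised to these reference arms may not reflect the wider melanoma population.

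**Working it through.** **Inputs.** From Table 5.4.7.2-1 (CA209067, nivolumab): overall 141/316, PD-L1 ≥ 1% 94/171, PD-L1 < 1% 41/117. Arm size 60 (Section 5.2). Two-sided 60% CI, so 20% in each tail (Section 10.3.1).

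**Reproducing the table.** 141/316 = 44.6%, 94/171 = 55.0%, 41/117 = 35.0%, matching the printed 45%, 55% and 35%. The difference is 19.9 points (95% Wald CI 8.5 to 31.3).

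**The unlisted patients.** 316 − 171 − 117 = 28 patients have no PD-L1 row, with 141 − 94 − 41 = 6 responders. This trial pools indeterminate with < 1%. If all 28 were indeterminate, that stratum would be (41 + 6)/(117 + 28) = 47/145 = 32.4%, and the gap 22.6 points. The table does not say what these 28 were, so both versions are carried.

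**Expected nivolumab ORR at a PD-L1 ≥ 1% share f.** f × 94/171 + (1 − f) × L, with L = 41/117 or 47/145. A 10-point change in f moves it by 0.10 × 19.9 = 2.0 points or 0.10 × 22.6 = 2.3 points.

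**Assumed rule.** An arm passes if the lower limit of its 60% CI exceeds the reference. At n = 60, Clopper-Pearson and Wald limits give the same cut-offs: 31/60 for a reference of 141/316 (or 0.45) and 28/60 for 0.40. The entries below are exact binomial chances that an arm no better than nivolumab passes. The first figure pools the 28 with < 1% and the second leaves them out.

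| PD-L1 ≥ 1% share | Expected nivolumab ORR | Passes, reference 141/316 | Passes, reference 0.40 |
|---|---|---|---|
| 40% | 41.4% / 43.0% | 7% / 11% | 24% / 33% |
| 54% | 44.6% / 45.8% | 17% / 22% | 42% / 50% |
| 60% | 45.9% / 47.0% | 22% / 28% | 51% / 57% |
| 70% | 48.2% / 49.0% | 34% / 39% | 64% / 69% |

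The nominal level is 20%. The historical share is 171/316 = 54% of all nivolumab patients, or 171/288 = 59% of those with a listed result. In the 0.40 column much of the excess comes from a reference below the CA209067 rate. Within each column, the rise from top to bottom is the case-mix effect.

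**Effect on a truly active arm.** If an arm matched the ipilimumab plus nivolumab rates in the same table (68/123 and 101/155), it would reach 31/60 with probability 0.91 at a 40% share and 0.96 at 70%. The main effect is on false positives.

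**How far chance alone moves the mix.** At f = 0.54 the SD of the share is √(0.54 × 0.46/60) = 6.4 points; at f = 0.594 it is 6.3. Multiplied by 0.199 or 0.226, this is about 1.3 to 1.5 ORR points.

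**With a standardised reference.** At shares of 40%, 54%, 60% and 70% the cut-offs become 29, 31, 32 and 33 responders with the 28 pooled (exact error 17%, 17%, 15%, 18%), or 30, 32, 32 and 34 with them left out (17%, 15%, 20%, 15%). None exceeds 20%.

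**The case against.** The strongest reply is that the consequence is limited and much of the arithmetic is conditional. The visible text contains no rule that an arm succeeds when its interval clears the reference; Table 4-4 asks for estimates, intervals and p-values. The reference is redacted and could be near 40% or 45%, a choice that matters as much as case mix. No PD-L1 shift is documented. A 70% share is 16 points above 54%, or 2.5 SDs (16/6.4), so it would need systematic selection. The objective is labelled preliminary, the design is an exploratory proof of concept, and Arm D gives a concurrent arm randomised within the same strata. Section 10.3 defers detail to an SAP to be signed before database lock, so standardisation may yet appear there.

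All of this stands as a limit on size. It does not remove the dependence. Arm D contains ipilimumab, so it cannot show what the combination adds to nivolumab alone, and nothing visible adjusts the comparison with the constant.

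A reader might infer that Section 5.4.7.2 contradicts Section 5.4.8 by saying "This pattern of response rate was consistent regardless of PD-L1 expression levels". It does not: that sentence concerns the ordering of the three regimens, which does hold at both PD-L1 levels. A reader might also take 32% as the established rate for this trial's lower stratum. That requires all 28 unlisted patients to have been indeterminate, and Section 9.8.2 defines the term narrowly (staining obscured, with enough evaluable cells).

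**Conclusion.** The point holds as a dependence on case mix, not as a demonstrated bias. A single historical constant serves a primary comparison whose true benchmark moves by about 2.0 to 2.3 ORR points for every 10 points of PD-L1 ≥ 1% share. Under the assumed interval rule and a reference of 141/316, the false-pass chance runs from 7–11% at a 40% share to 34–39% at 70%; with a reference of 0.40 it runs from 24% to 69% across the same shares and both treatments of the 28 patients.

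These figures rest on an assumed success rule, an assumed reference, 60 patients per arm, and CA209067 stratum rates taken as true. Two stronger readings are not supported. The documents do not show that the enrolled mix has shifted, so it cannot be said that the result will mislead. Nor is real activity likely to be hidden, since an arm performing like ipilimumab plus nivolumab would pass at least 90% of the time at these shares under the 141/316 reference.

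**What to change.** Prespecify in the SAP, beside the fixed value, a comparison of each of Arms C and F with a standardised reference: (observed share ≥ 1%) × 55% + (observed share < 1% or indeterminate) × the matching historical rate. Take that second rate from the sponsor's CA209067 data using this trial's definition of indeterminate. Until it is available, show the range from 35% (table row alone) to 32% (all 28 unlisted patients counted as indeterminate). State that the efficacy conclusion rests on whether the fixed and standardised comparisons agree.

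The cost is SAP wording and one formula. PD-L1 is already assessed centrally before randomisation, so no new data are needed. The drawback is sampling error in the subgroup rates. The standardised reference has variance f² × p₁(1 − p₁)/171 + (1 − f)² × L(1 − L)/m, where p₁ = 94/171 and m is 145 or 117. Over shares of 40% to 70% its SE is about 2.7 to 2.9 points with the 28 pooled and about 2.9 to 3.1 with them left out, against 2.8 for the overall rate, √(0.446 × 0.554/316). So little precision is lost. M-stage and permitted prior adjuvant therapy stay unadjusted, because the documents give no nivolumab ORR by either; the SAP should say so.
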